#### 10.2.2. Percentage Change From Baseline in RSV Viral Load

Change in  $\log_{10}$  viral load from baseline will be calculated to 60 hours and 156 hours after first dose, both for total RSV viral load by RT-qPCR and for RSV viral load by CBIA. No imputation of missing data is planned, but prior to unblinding a check will be made to determine the amount of missing data at 60 and 156 hours and whether an imputation method is warranted.

For Part B, comparisons will be made between RV521 and placebo using a mixed effects ANCOVA model on the change from baseline including a random effect term for subject, fixed effect terms for treatment group, age group ( $\geq 1$  month to  $< 6$  months or  $\geq 6$  months to  $\leq 36$  months at screening) and presence or absence of other known respiratory pathogens at baseline, and baseline RSV viral load as a covariate. The model will be fitted to the 24 subjects treated at the final doses selected for Cohort 5 (see Section 6.1).

Furthermore, the above analysis will be repeated but also including a treatment group by presence or absence of the other known respiratory pathogens at baseline interaction, in order to investigate the treatment effect given the presence or absence of the pathogens.

For Part C, comparisons will be made between RV521 and placebo using a mixed effects ANCOVA model on the change from baseline including a random effect term for subject, fixed effect terms for treatment group, presence or absence of other known respiratory pathogens at baseline, duration of symptoms prior to randomisation and severity of illness at randomisation, and baseline RSV viral load as a covariate.

For both Parts B and C the change from baseline least square mean (lsmean) estimates will be presented for  $\log_{10}$  viral load, along with the difference in lsmeans between RV521 and placebo and 95% confidence intervals. In addition the lsmean change from baseline will be back transformed and presented as a percentage change from baseline of the original viral load. Estimates will also be provided separately by presence or absence of other known respiratory pathogens at baseline.

Distributional assumptions underlying the statistical analyses will be assessed by visual inspection of residual plots. Normality will be examined by normal probability plots, while homogeneity of variance will be assessed by plotting the residuals against the predicted values for the model. If the distributional assumptions of a normal distribution in the parametric approach are not satisfied, investigations into influence of outliers or non-parametric methods will be considered.

This document is confidential.

10.2.3. CCI [REDACTED]

[REDACTED]

[REDACTED]

[REDACTED]

This document is confidential.

11. CCI [REDACTED]

11.1. [REDACTED]

[REDACTED]

[REDACTED]

[REDACTED]

- | [REDACTED]
- | [REDACTED]
- | [REDACTED]
- | [REDACTED]
- | [REDACTED]

CCI [REDACTED]

11.2. CCI [REDACTED]

[REDACTED]

[REDACTED]

This document is confidential.

## 12. Safety

The population used for safety analyses will be the Safety Population. Safety will be assessed on the basis of AE reports, clinical laboratory data, ECG parameters, physical examinations, and vital signs.

### 12.1. Extent of Exposure

For Study Part A, the number and percentage of subjects with the planned dose administered and the number and percentage of subjects with the planned dose not administered will be summarised for all analysis populations. For Study Parts B and C for all analysis populations, duration of exposure to IMP in days will be summarised as a continuous variable, total number of doses administered will be summarised as a categorical variable, and the numbers and percentages of subjects with all planned doses administered and at least one planned dose not administered will be summarised. For the subjects with at least one planned dose not administered, the number of doses where the planned dose was not administered will be summarised as a categorical variable. Duration of exposure will be calculated from first and last dose times and presented to 1 decimal place. No account will be taken of gaps in medication. All collected IMP administration details and calculated extent of exposure variables, including total volume administered in mL, will be listed for the Safety Population.

### 12.2. Treatment Compliance

Number of doses where planned dose not administered and number of doses missed will be presented in a data listing for the Safety Population to assess treatment compliance.

### 12.3. Adverse Events

The Investigator will document all AEs that occur during the study from the time the ICF is signed until the last follow up Visit on the appropriate page of the CRF. Each separate AE episode will be recorded. For example, if an AE resolves completely or resolves to baseline and then recurs or worsens again, this will be recorded as a separate AE. For AEs to be considered intermittent, the events must be of similar nature and severity.

Severity of AEs will be assessed by the Investigator using the National Cancer Institute (NCI) Common Terminology Criteria for AEs (CTCAE) v5.0, 27 November 2017 (CTCAE v5.0). Grades of the NCI CTCAE refer to the severity of the AE as follows:

- Grade 1 Mild; asymptomatic or mild symptoms; clinical or diagnostic observations only; intervention not indicated.
- Grade 2 Moderate; minimal, local or non-invasive intervention indicated; limiting age-appropriate instrumental Activities of Daily Living (ADL).
- Grade 3 Severe or medically significant but not immediately life-threatening; hospitalisation or prolongation of hospitalisation indicated; disabling; limiting self-care ADL.
- Grade 4 Life-threatening consequences; urgent intervention indicated.
- Grade 5 Death related to AE.

For purposes of this study the severity will be graded as follows:

- Grade 1: Mild
- Grade 2: Moderate
- Grade 3>: Severe

This document is confidential.

If there is a change in severity of an AE, every episode of the AE will be captured separately and all required information for every episode will be provided separately.

AEs will be coded according to the MedDRA dictionary Version 22.1. Summary tables of AEs will be based on TEAEs, defined as events starting, or worsening, after the first dose of IMP. Treatment-related TEAEs will be defined as TEAEs with causality assessed as possibly, probably, or definitively related to IMP.

In order to assign treatment-emergence, AEs with missing or partial dates are considered treatment-emergent unless there is clear indication that the event occurred before the first dose of IMP. In general, only TEAEs will be included in the summary tables, but all AEs will be included in the data listings.

At each level of summarisation, summaries will include the number and percentage of subjects. For summaries by MedDRA System Organ Class (SOC) and PT, a subject will be counted once at the SOC level and once at each PT within the SOC level. For summaries by SOC, PT, and severity, a subject will be counted once at each severity level for which the event occurred at the SOC level and at each severity level for which the event occurred for each unique PT within that SOC level. Therefore, subjects may contribute to multiple severity levels within a PT or SOC. For summaries by SOC, PT, and maximum severity, a subject will be counted once at the highest severity level for which the event occurred at the SOC level and the highest severity level for each unique PT within that SOC level. Therefore, subjects may only contribute once to each PT and once to each SOC level. AEs with missing severity will be counted as severe. Summaries by maximum relationship will be handled similarly to the summaries by maximum severity. AEs with missing relatedness will be counted as definitively related.

Summaries presenting frequency of AEs by SOC and PT will be ordered by overall descending frequency of SOC and then, within a SOC, by overall descending frequency of PT.

The following tables will be produced:

- An overall summary of the number and percentage of subjects reporting TEAEs, serious TEAEs, treatment-related TEAEs, TEAEs leading to permanent discontinuation of IMP and TEAEs leading to death.
- TEAEs overall and by SOC and PT.
- TEAEs overall and by SOC, PT and severity.
- TEAEs overall and by SOC, PT and maximum severity.
- TEAEs overall and by SOC, PT and maximum relationship to IMP.
- Treatment-related TEAEs overall and by SOC and PT.
- Serious TEAEs, overall and by SOC and PT.
- TEAEs leading to permanent discontinuation of IMP, overall and by SOC and PT.

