7 STUDY OBJECTIVES

7.1 PART A and PART B

7.1.1 Primary Objective

Primary Objective	Primary Endpoints
To evaluate the safety and tolerability of single (Part A) and multiple (Part B) oral doses of RV521 in infants hospitalised with RSV LRTI	
Safety and tolerability parameters to be assessed will include, but are not limited to:
 
 • AEs, TEAEs, SAEs, and withdrawals due to TEAEs • Physical examinations • Vital sign parameters (ie, systolic and diastolic BP, temperature, RR, HR, and pulse oximetry), and changes from baseline in these parameters at predefined time points • Laboratory tests (haematology, chemistry, and urinalysis test results) and changes from baseline in these parameters, at predefined time points • ECG measurements and changes from baseline in these parameters at predefined time points

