9.5 Duration of Treatment

Part A:

Subjects will participate for up to 8 days. A single oral dose of RV521 will be administered in Part A, and the visit schedule will include:

- Screening Visit (-24 hours)
- Dosing Visit 1 (-2 pre-dose to 18-24 hours post-dose)
- Post-dosing Visit 2 (48 hours post-dose)
- Telephone Follow-up (Day 7)

Part B:

Subjects will participate for up to 13 days. The proposed dosing regimen for Part B is RV521 or placebo administered BID, 12 hours apart, for a period of 5 consecutive days (for a total of 10 doses), and the visit schedule will include:

- Screening Visit (-24 hours)
- Dosing Visit 1 (-2 to 18-24 hours post-dose)
- Dosing Visit 2
- Dosing Visit 3
- Dosing Visit 4
- Dosing Visit 5
- Follow-Up Visit Day 7 (+40-48 Hours Post-Dose 10)
- Telephone Follow-Up (Day 12)

Note: The actual day of each Dosing Visit will be dependent upon the time that the subject receives their first dose of IMP on Visit 1. Follow-Up Visit Day 7 may therefore fall on Study Days 7 or Day 8 depending upon the time the subject received his or her first dose of IMP on Dosing Visit 1.

Part C:

Subjects will participate for up to 35 days, and the visit schedule will include: Screening (24 hours to first dose), Dosing Visits 1 to 5 (5 days), and follow-up 40-48h Post-Dose 10 (Study

Days 7 or 8) and at Study Days 14 and 34. Inpatient duration will be determined clinically by the PI or other health care provider and by ability to complete study procedures and assessments on an outpatient basis ([Section 9.4](#)). Follow-up days are expected to be on an outpatient basis.

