11.1.6 Safety Variables

Adverse events will be coded according to the current version of MedDRA. Summary tables of AEs will be based on TEAEs, defined as events starting, or worsening, after the first dose of IMP. Summaries, by MedDRA SOC and Preferred Term, will be provided for all TEAEs, all treatment-related TEAEs (with causality assessed as possibly, probably or definitively related to IMP), all serious TEAEs and all AEs leading to early discontinuation from the study. Summary tables by maximum severity and maximum relationship, and by intensity per CTCAE will be presented.

For laboratory tests, ECG measures and vital signs parameters, baseline will be defined as the last non-missing result prior to the first dose of IMP. Results at each visit will be summarised using the statistics: n (number of observations), mean, SD, median, minimum and maximum. In addition, change from baseline from all safety parameters will also be summarised by post-baseline visits.

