## 4. Endpoints

### 4.1. Primary Endpoints

Safety and tolerability parameters to be assessed for study Parts A and B will include, but are not limited to:

- AEs, treatment emergent AEs (TEAEs), serious AEs (SAEs), and withdrawals due to TEAEs
- Physical examinations
- Vital sign parameters (i.e., systolic and diastolic blood pressure, temperature, respiratory rate, heart rate, and pulse oximetry), and changes from baseline in these parameters at predefined time points
- Laboratory tests (haematology, chemistry, and urinalysis test results) and changes from baseline in these parameters, at predefined time points
- ECG measurements and changes from baseline in these parameters at predefined time points

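### The SAP has no TEAE-level summary of study withdrawals, although these are part of the Parts A/B primary safety endpoint, and its AE severity tables pool Grade 3 and above

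*SAP*

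**What the plan says.** The primary safety endpoint for Parts A and B is defined in the same terms in both documents. Protocol 7.1.1 lists "AEs, TEAEs, SAEs, and withdrawals due to TEAEs" and SAP 4.1 lists "AEs, treatment emergent AEs (TEAEs), serious AEs (SAEs), and withdrawals due to TEAEs".

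For the tables, Protocol 11.1.6 plans summaries by SOC and PT that include "all serious TEAEs and all AEs leading to early discontinuation from the study". It adds that tables by maximum severity, by maximum relationship "and by intensity per CTCAE will be presented".

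SAP 12.3 sets out a different list. Its discontinuation table is "TEAEs leading to permanent discontinuation of IMP, overall and by SOC and PT", and the overall AE summary uses the same IMP-based category. The table index repeats it for each part (Tables 14.3.1.1.8, 14.3.1.2.8 and 14.3.1.3.8), as does Listing 14.3.2.4. No AE table or AE listing is defined by withdrawal from the study.

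On severity, SAP 12.3 first reproduces the five CTCAE grades and then states "For purposes of this study the severity will be graded as follows", followed by three levels: mild, moderate, and a top level written as Grade 3 with a greater-than sign. AEs with no recorded severity go into the severe level.

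**The concern.** Stopping IMP and leaving the study are different events, and the endpoint is written in terms of the second. A TEAE table built on the first does not report the endpoint component. In Part A it can report almost nothing, because the treatment is over before a TEAE can arise.

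The severity grouping is a separate departure from Protocol 11.1.6. The top row of the AE severity tables can mix Grades 3, 4 and 5 with events that were never graded, so a reader cannot tell severe from life-threatening in those tables.

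At stake is whether the clinical study report answers its own primary safety question directly, by event term and on the Safety Population, or leaves the reader to assemble the answer from disposition tables and listings.

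**Working it through.** No sample size, power or error rate is involved, so the check sets the texts side by side.

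**1. Endpoint against table**

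| Item | Protocol | SAP |
|---|---|---|
| Primary endpoint component, Parts A/B | Withdrawals due to TEAEs (7.1.1) | Same (4.1) |
| Planned SOC/PT table | "all AEs leading to early discontinuation from the study" (11.1.6) | Permanent discontinuation of IMP only (12.3) |
| AE severity | Includes CTCAE intensity (11.1.6) | Three levels, Grade 3 and above pooled (12.3) |

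The SAP keeps the endpoint but changes the table meant to report it.

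**2. Part A**

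The protocol states "A single oral dose of RV521 will be administered in Part A" (9.5). Both documents define a TEAE as starting or worsening after the first dose. In Part A the first dose is also the last, so no later dose remains to be discontinued. With 12 to 24 infants planned, the expected content of Table 14.3.1.1.8 is 0 of 12 to 24, however many infants are withdrawn because of a TEAE. The exception is an event during an incompletely ingested dose, a situation that Protocol 8.4.5 recognises.

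**3. Parts B and C**

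At 12-hour intervals, Dose 10 falls 9 × 12 = 108 hours (4.5 days) after Dose 1, that is on Day 5 or 6 if Day 1 is the day of Dose 1. Follow-up runs to Day 12 in Part B and Day 34 in Part C:
- Part B: 12 − 6 = 6 to 12 − 5 = 7 days with no IMP left to stop.
- Part C: 34 − 6 = 28 to 34 − 5 = 29 days with no IMP left to stop.

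A withdrawal due to a TEAE in that window would not appear in an IMP-discontinuation table. Protocol 8.5.6.2 also shows that stopping treatment and leaving the study are separate: a subject who needs a prohibited medication stops treatment and stays in the study.

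**4. What the disposition tables supply**

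SAP 7.1 summarises withdrawals with reasons in every part (Tables 14.1.1.1 to 14.1.1.3), and Protocol 8.4.4 lists AEs among the withdrawal reasons. Three differences from the endpoint remain:
- The tables cover all subjects in the database, not the Safety Population.
- AEs are collected from consent (Protocol 10.1.3.1), so a withdrawal for a pre-dose AE could be counted although it is not a TEAE.
- The event is not named.

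**5. What the severity pooling loses**

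- Grade 5: recoverable from the line for TEAEs leading to death and from the deaths listing (14.3.2.1).
- Laboratory Grade 4: kept apart from Grade 3 in SAP 12.4.
- Other Grade 4 AEs: no separate summary by grade. Many should appear in the serious-TEAE tables, but those do not show grade.

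**6. Whether the changes are declared**

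The legible text of SAP 14 lists other departures from the protocol and neither of these. Part of that section is redacted, so their absence cannot be confirmed.

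**The case against.** The strongest reply is that nothing is lost. Withdrawals with reasons are counted in every part, and all AEs are listed (Listing 16.2.7.1). Deaths and serious TEAEs have their own outputs. A SOC/PT breakdown adds little for 12 to 24 single-dose infants. This stands as a limit on the size of the point. A reader might infer that a primary safety component will be reported as zero in Part A whatever happens. The documents do not support that: the Part A disposition table will show an AE withdrawal. Only the TEAE-level table is empty.

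A reader might also infer that life-threatening or fatal events are concealed, or that part of the primary endpoint is hidden by the pooling. Neither follows. Deaths are shown separately. The protocol's life-threatening criterion for an SAE is close in wording to CTCAE Grade 4, so most such events should reach the serious-TEAE tables. Grade is not a named component of the primary endpoint. The protocol synopsis promises only maximum severity and maximum relationship; the CTCAE-intensity summary is in 11.1.6 alone.

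Nor do the documents show that pooling would mislead dose selection. Dose decisions run through DSMC outputs set in the DSMC Charter, and the Part C pausing rule in Protocol 8.4.5 itself uses Grade 3 or higher.

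An IMP-discontinuation table is also useful in Parts B and C. It captures the child who stops treatment and stays in the study, and it may satisfy the Part C endpoint, which refers only to discontinuations due to AEs. That argues for keeping it there, not for letting it stand in for study withdrawal.

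Finally, Protocol 11.1 allows SAP amendments for Parts B and C before database lock. That leaves room to make the change.

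**Conclusion.** The point holds as a mismatch between a stated primary-endpoint component and the planned AE tables. There is no TEAE-level summary of study withdrawals in any part. The Part A substitute is empty almost by construction (0 of 12 to 24), and the Parts B and C substitutes cannot register a withdrawal due to a TEAE after Dose 10. The number of infants affected cannot be estimated, because the documents give no expected rate of AE withdrawal.

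The severity pooling is a smaller departure from Protocol 11.1.6. Five grades become three levels, and what is lost is a summary that separates Grade 4 from Grade 3 for non-laboratory AEs. It does not empty the primary endpoint.

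This is a change that should be made, but it is not evidence that safety outcomes go unreported. It assumes that the SAP's top severity level means Grade 3 or higher, since the notation is unclear, and that the redacted part of SAP 14 does not declare these changes.

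**What to change.** In SAP 12.3 and the table index:

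- Add TEAEs leading to withdrawal from the study to the overall AE summary, and as a SOC/PT table for Parts A, B and C, on the Safety Population and linked to the CRF withdrawal reason.
- Keep the IMP-discontinuation table for Parts B and C, and drop Table 14.3.1.1.8 for Part A.
- Tabulate AE severity and maximum severity by CTCAE Grades 1 to 5, with missing grades in a row of their own so that they do not inflate a graded row.
- If the sponsor prefers the present tables, declare and justify both changes in SAP 14.

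The cost is a few table shells and some programming. The action-taken categories in Protocol 10.1.3.1 have no option for withdrawal from the study, so the link between the AE record and the disposition record must be defined and programmed. The documents do not describe such a link. Provided the CRF stores the CTCAE grade that investigators are asked to assign, and the withdrawal reason can be traced to an AE, no new data collection is needed.

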#### **12.4. Laboratory Evaluations**

Laboratory results will be presented for haematology, chemistry and urinalysis.

This document is confidential.

All laboratory results will be converted to Standard International units. Results below or above the normal range will be indicated in the listings.

In the presence of re-tests, original results will be used in the summary tables, however all re-test results will be included in the listings.

For each of Parts A, B and C, continuous laboratory results will be summarised at baseline and at each scheduled post-baseline time point. Summary statistics will be provided for the observed values at each time point, and the corresponding change from baseline. Categorical laboratory results for urinalysis will be summarised at baseline and at each scheduled post-baseline time point. The number and percentage of subjects with laboratory measurements outside of the normal reference range will also be summarised at baseline and at each scheduled post-baseline time point.

Laboratory results will be graded according to NCI CTCAE v5.0, for applicable parameters (haemoglobin, white blood cells, platelets, creatinine, AST, ALT, alkaline phosphatase, lactate dehydrogenase, total bilirubin). The severity will be graded as follows:

- Grade 1: Mild
- Grade 2: Moderate
- Grade 3: Severe
- Grade 4: Life-threatening

For each applicable parameter, the number and percentage of subjects experiencing each abnormality at any time after first dose will be summarised by severity grade and by maximum severity grade.

Shift tables of laboratory results from baseline to maximum post-dose severity grade, including unscheduled visits, will be presented.

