- ^t It is not necessary to repeat the assessment for the -2h to 0 h Pre-Dose 1 timepoint, if the assessment was carried out for screening purposes within the 2 h Pre-Dose 1. However, if the screening assessments were carried out >2 h prior to Dose 1 for screening purposes (i.e. within the first 22 hours of the screening window), the assessment must be repeated between -2h to 0 h Pre-Dose 1.
- ^u Allowed time window on the end of treatment safety bloods and urinalysis is +/- 2 days. Should a subject be discharged after Dose 10, the safety blood sample should be obtained prior to discharge, particularly if the parents/legal guardians are unlikely to return for the next visit.
- ^{*} **Procedure to be done if subject is in the hospital.**

Table 3b. Schedule of Assessments for Part C subjects discharged prior to Dosing Visit 3

Assessment	Screening	Treatment Phase									Post-Treatment Phase		
	Screening Visit	Dosing Visit 1			Dosing Visit 2		Dosing Visit 3	Dosing Visit 4	Dosing Visit 5	Follow Up			
		Dose 1	Dose 2	Dose 3	Dose 4	Doses 5 and 6	Doses 7 and 8	Doses 9 and 10	Visit Day 7	Visit Day 14±1 Day	Visit Day 34±1 Day		
Time Relative to Dose	-24 h to first dose	-2 h to 0 h	0 h	4-5 h Post-Dose							+40-48 h Post-Dose 10	Day 14	Day 34
Written Informed Consent ^a	X												
Inclusion / Exclusion Criteria	X	X ^c											
RSV Rapid Diagnostic Test	X ^b												
Demographics ^d	X												
Medical History	X												
Prior Medication Review	X												
Physical Examination ^e	X	X ^c									X		
Hydration Status ^f	X	X ^c				X ^g		X ^g	X ^g	X ^g	X		
Body Weight / Length / Head Circumference	X										X	X	X
Vital Signs ^h	X	X ^c		X	X	X	X	X ⁱ	X ⁱ	X ⁱ	X	X	X
12-Lead ECG ^j	X			X		X		(X ^k)	(X ^k)		X		
ReSVinet Score for Clinicians ^l	X	X ^c				X		X ^m	X ^m	X ^m	X	X	X
Record RSV Signs and Symptoms ⁿ	X	X ^c			X	X	X	X ^o	X ^o	X ^o	X	X	X
Record Supplemental O ₂		X			X	X	X	X	X	X			

Assessment	Screening	Treatment Phase									Post-Treatment Phase		
	Screening Visit	Dosing Visit 1			Dosing Visit 2		Dosing Visit 3	Dosing Visit 4	Dosing Visit 5	Follow Up			
		Dose 1	Dose 2	Dose 3	Dose 4	Doses 5 and 6	Doses 7 and 8	Doses 9 and 10	Visit Day 7	Visit Day 14±1 Day	Visit Day 34±1 Day		
Time Relative to Dose	-24 h to first dose	-2 h to 0 h	0 h	4-5 h Post-Dose							+40-48 h Post-Dose 10	Day 14	Day 34
Pulse Oximetry on Room Air		X			X	X	X	X	X	X			
Adapted ReSVinet Scale for Parental Use ^p	X					X		X	X	X	X	X	X

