10.1.3.4 Clinical Laboratory Assessments

The following laboratory safety tests will be performed according to the relevant Schedule of Assessments for Part A (Table 1), Part B (Table 2), and Part C (Table 3a inpatients and Table 3b outpatients) in Section 8.1. Clinically significantly abnormal laboratory finding should be followed up until resolution or until the analyte is stable. If the post-treatment data is reported as invalid, an unscheduled visit should be performed to repeat the laboratory safety tests within 2 weeks after Dose 10.

Haematology

Haemoglobin, haematocrit, white blood cell count (total and differential), red blood cell count, platelet count, mean cell volume (MCV), mean cell haemoglobin (MCH), and MCH concentration (MCHC).

Clinical Chemistry

Creatinine, urea (or blood urea nitrogen), AST, ALT, gamma glutamyltransferase, alkaline phosphatase, lactate dehydrogenase, total bilirubin, albumin, total protein, sodium, potassium, chloride, glucose, and calcium.

Note: for the Screening Visit ONLY, AST and ALT analysis can also be conducted at the local laboratory, although a blood sample must also be sent to the Central laboratory for analysis.

Urinalysis

pH, glucose, ketones, blood, protein, and microscopy.

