## 6. General Aspects for Statistical Analysis

### 6.1. General Methods

- Unless otherwise specified, summaries for Part A will be presented by cohort, dose level and overall, summaries for Part B will be presented by cohort, treatment, dose level and overall, and summaries for Part C will be presented by treatment and overall.
- Unless otherwise specified, continuous variables will be summarised using the number of observations (n), mean, standard deviation (SD), median, minimum, and maximum. Means and medians will be presented with one more decimal than the observed values. SD values will be presented with 2 more decimals than the observed values.
- Unless otherwise stated, categorical variables will be summarised using number of observations (n), frequency and percentages of subjects.
- Presentations for PK data are described separately in Section 9. Presentations for PD data are described in Section 10.
- All relevant subject data will be included in listings. All subjects entered into the database will be included in subject data listings.
- All statistical testing will be 2-sided with an alpha level of 0.05, with no adjustment for multiple comparisons.
- For Part B, formal statistical testing will focus on the 24 subjects treated at the doses used in Cohort 5 that were identified in Cohorts 3 and 4. These 24 subjects comprise the whole of Cohort 5, plus the 4 subjects from each of Cohorts 3 and 4 that were randomized with the selected dose/placebo.
- Where there are multiple assessments at a given time point, only the results recorded on the scheduled time point page of the case report form (CRF) will be used for summarisation, unscheduled assessments will be listed only.

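### When the Visit Day 7 safety laboratory sample is invalid, the SAP keeps the protocol-ordered repeat out of the by-visit and change-from-baseline tables in Parts B and C

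*SAP*

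**What the plan says.** Protocol section 10.1.3.4 deals with post-treatment laboratory data that are reported as invalid. In that case "an unscheduled visit should be performed to repeat the laboratory safety tests within 2 weeks after Dose 10".

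SAP section 12.4 says how laboratory data are tabulated. On repeats: "In the presence of re-tests, original results will be used in the summary tables, however all re-test results will be included in the listings". On the scope of the main tables: "continuous laboratory results will be summarised at baseline and at each scheduled post-baseline time point". The urinalysis-category and out-of-reference-range tables have the same scheduled-time-point scope.

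Two kinds of table in that section are wider. One counts graded abnormalities: "the number and percentage of subjects experiencing each abnormality at any time after first dose will be summarised by severity grade". The other is explicit about unscheduled data: "Shift tables of laboratory results from baseline to maximum post-dose severity grade, including unscheduled visits, will be presented".

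SAP section 6.1 gives the general rule. Where a time point has several assessments, "only the results recorded on the scheduled time point page of the case report form (CRF) will be used for summarisation", and "unscheduled assessments will be listed only".

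**The concern.** Keeping the original over a re-test is ordinary practice when the original is usable, because it stops favourable repeats from displacing real findings. Here the protocol asks for the repeat because the original cannot be used. If the repeat is then confined to listings, the infant has been brought back and sampled again, and the result is absent from the tables that most readers will look at.

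Laboratory results and their changes from baseline are a primary safety endpoint in Part B (protocol section 7.1.1, SAP section 4.1). In Part C the matching endpoint is clinically significant laboratory change, so by-visit means matter less there, although the same tables are planned.

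**Working it through.** There is no planned figure to reproduce. The check traces one infant with an invalid Visit Day 7 sample through the stated rules.

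**1. Scheduled laboratory time points.** Protocol Tables 2, 3a and 3b and SAP Tables 2 and 3 all place safety bloods and urinalysis at Screening and Visit Day 7 only. No other scheduled post-baseline value can fill the gap. The repeat instruction is tied to Dose 10, so it concerns Parts B and C, not single-dose Part A.

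**2. Where the valid repeat goes under SAP sections 6.1 and 12.4.**

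- Observed values and change from baseline: scheduled time points only, so excluded.
- Urinalysis categories: scheduled time points only, so excluded.
- Results outside the reference range: scheduled time points only, so excluded.
- Abnormalities by grade and by maximum grade: any time after first dose, so arguably included, though the SAP does not say so. Graded parameters only.
- Shift tables to maximum post-dose grade: unscheduled visits included. Graded parameters only.
- Listings: included.

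**3. Which analytes have the shift-table route.** SAP section 12.4 grades nine parameters: haemoglobin, white cells, platelets, creatinine, AST, ALT, alkaline phosphatase, lactate dehydrogenase and total bilirubin. Protocol section 10.1.3.4 lists 15 chemistry analytes. Six are graded, leaving 15 - 6 = 9 without the route: urea, gamma glutamyltransferase, albumin, total protein, sodium, potassium, chloride, glucose and calcium. In haematology, the haematocrit, red cell count, red-cell indices and white-cell differential are ungraded. No urinalysis item is graded.

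**4. Any other rule that would place the repeat.** SAP section 6.3 has no laboratory provision. SAP section 6.4 covers PK and PD sampling only. Nothing maps an unscheduled laboratory result to Visit Day 7.

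**5. Could the visit window absorb the repeat?** The protocol states: "Allowed time window on the end of treatment safety bloods and urinalysis is +/- 2 days". Visit Day 7 is 40 to 48 h after Dose 10, so the window closes at the latest at 48 + 48 = 96 h, or 4 days after Dose 10. The repeat is allowed up to 14 days (336 h) after Dose 10. The longest delay from the planned visit is about 336 - 48 = 288 h, or 12 days. A repeat taken between 4 and 14 days after Dose 10 falls outside the window.

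**6. Weight of one affected infant.** The planned Part B numbers treated are 16 to 28 on RV521 and 8 to 12 on placebo (protocol section 8.4.1).

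- RV521: 1/28 = 3.6% to 1/16 = 6.3% of the group.
- Placebo: 1/12 = 8.3% to 1/8 = 12.5% of the group.
- Part C, with 37 per arm: 1/37 = 2.7% of an arm.

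SAP section 6.1 also presents Part B by cohort, treatment and dose level. In a Cohort 3 or 4 dose group of four randomised 3:1, one invalid sample leaves 2 of 3 RV521 values or 0 of 1 placebo values.

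**The case against.** The strongest reply is that both SAP rules choose between competing results. The re-test rule most naturally presumes a usable original, and the rule in section 6.1 opens with the condition that a time point has multiple assessments. On that reading the SAP is silent on invalid originals; it does not order their use. That is fair, but it does not rescue the repeat: the restriction to scheduled post-baseline time points in section 12.4 applies whichever way the re-test rule is read, and a repeat taken at an unscheduled visit does not meet it.

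A second reply is that section 12.4 already admits unscheduled visits to the shift tables. This stands for the nine graded parameters and limits the point. It does nothing for the other analytes or for urinalysis, and it does not supply a change from baseline.

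A third reply is that leaving late repeats out of by-visit means is defensible: a value up to about 12 days late is further off drug and could dilute a transient signal. This also stands, as a reason to flag and count substituted values. It is not a reason to leave the choice unstated.

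Finally, no hypothesis test, type I error or efficacy conclusion is touched. That is correct.

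**Conclusion.** The gap is real and limited. Under the stated rules, an infant in Part B or C with an invalid Visit Day 7 sample has no valid post-baseline value in the four kinds of scheduled-time-point table, even though the protocol obtained one. This assumes that the repeat is recorded as unscheduled, as the protocol describes it. The documents give no invalid-sample rate. Multiplying an assumed rate by the arm sizes would only return the assumption, so the number of infants affected is left open. The correction is worth making because the Part B groups are small and the endpoint is primary there.

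A reader might infer more, in three ways that the documents do not support:

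- **That the infant's only post-baseline laboratory value is lost altogether.** It stays in the listings and, for graded parameters, in the shift tables.
- **That an invalid number will be tabulated.** This is possible, but nothing says that a result reported as invalid keeps a reportable value.
- **That the by-visit and shift tables contradict each other.** One describes a scheduled time and the other the worst grade after dosing. Section 12.4 states the different scopes openly.

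**What to change.** Add to SAP section 12.4, with a matching exception in section 6.1:

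- Where the scheduled post-treatment laboratory result is invalid or not reportable, the first valid protocol-ordered repeat is used as the Visit Day 7 value in the by-visit tables (observed values, change from baseline, urinalysis categories, out-of-range counts). It is flagged with its actual study day.
- Results declared invalid are listed only and are not graded.
- A valid original keeps precedence over any other re-test.
- Each affected table shows the number of flagged values.

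The cost is a few sentences and one derivation flag. No visit or sample changes. The downside is that some flagged values will lie outside the 2-day window and further off drug; the displayed count lets the reader judge how much that matters. Protocol section 11.1 allows SAP amendments for Parts B and C if they are signed off before database lock and unblinding of the part concerned.
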